9.3. Exclusion Criteria

Subjects who meet any one of the following criteria (Table 9.3-1) will be excluded from this clinical study.

Table 9.3-1: Exclusion Criteria

Clinical Exclusion Criteria

- History of spontaneous sustained VT (≥ 160 bpm at ≥ 30 seconds in duration) or VF not due to a reversible cause
- NYHA Class IV documented in the medical records within 90 calendar days prior to enrollment
- Subject is eligible and scheduled for cardiac resynchronization (CRT) implant
- Subjects with a previous subcutaneous ICD (S-ICD)
- Subject with existing TV-ICD device implanted for greater than 60 days
- Subjects with coronary artery bypass graft surgery or percutaneous coronary intervention within the past 90 calendar days prior to enrollment
- Subjects with documented myocardial infarction within the past 90 calendar days prior to enrollment
- Subjects on the active heart transplant list
- Subject who has a VAD or is to receive VAD
- Life expectancy shorter than 18 months due to any medical condition (e.g., cancer, uremia, liver failure, etc...)
- Subjects currently requiring hemodialysis
- Subject who is known to pregnant or plans to become pregnant over the course of the trial
- Subject is enrolled in any other concurrent clinical study, with the exception of local mandatory governmental registries and observational studies/registries, without the written approval from Boston Scientific

10. Subject Accountability

10.1. Point of Enrollment

Subjects who meet the eligibility criteria and agree to participate will be given written informed consent approved by the center's Institutional Review Board (IRB) / Ethics Review Committee (ERC).

All subjects who complete the informed consent process, sign and date the informed consent form are considered enrolled in the APPRAISE ATP study. No study related procedures can take place until the ICF is signed. Screening tests that are part of Standard of Care (SOC) can

be used to determine pre-eligibility. Subjects enrolled in this investigation must be followed per this investigational protocol.

10.2. Withdrawal

All subjects enrolled in the clinical study, including those withdrawn from the clinical study or lost to follow-up, shall be accounted for and documented. If a subject withdraws from the clinical investigation, the reason(s) shall be reported. Reasons for withdrawal include, but are not limited to:

- o Subject found not to meet eligibility criteria
- Subject did not get randomized
- Subject choice to withdraw consent
- o Device explanted and not replaced with a BSC TV-ICD
- o Subject was upgraded to a CRT-D system
- o VAD insertion or heart transplant
- o Investigator discretion
- o Enrollment ceiling met
- o Lost to follow-up, despite best efforts to locate the subject;
 - Three documented attempts to contact the subject, including one certified letter, are required to declare a subject lost to follow up.
- o Death (see Section 19.7 for reporting requirements)

If a subject withdraws from the clinical investigation, the reason(s) shall be reported on the End of Study electronic case report form (eCRF) in the EDC system. Data up to the point of withdrawal will be collected. All open adverse events should be closed or documented as chronic. Normal manufacturer vigilance monitoring of device performance will take place after a subject is withdrawn.

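### Section 10.2 lets subjects be withdrawn for CRT-D upgrade, VAD, transplant or explant, no later vital status is specified, and the all-cause death analysis censors them there

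*Combined protocol and SAP*

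**What the plan says.** Section 10.2 introduces its list with "Reasons for withdrawal include, but are not limited to". The list includes "Subject was upgraded to a CRT-D system", "VAD insertion or heart transplant", "Device explanted and not replaced with a BSC TV-ICD" and investigator discretion. It also includes death itself: "Death (see Section 19.7 for reporting requirements". No sentence makes withdrawal compulsory after any of these events, so a subject who is upgraded and not withdrawn stays in follow-up.

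On what follows withdrawal, the section says "Data up to the point of withdrawal will be collected" and "Normal manufacturer vigilance monitoring of device performance will take place after a subject is withdrawn". Neither sentence provides vital status.

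Section 12.1.3.2 censors survivors at withdrawal in the analysis of time to death. Section 12.1.2.2 does the same for subjects with neither shock nor death. Sections 12.1.1.3, 12.1.4.2 and 12.1.5.2 also censor the three shock endpoints at withdrawal. Section 12.2.1 puts all primary and secondary analyses on an intention-to-treat footing, and Section 11.9 keeps subjects reprogrammed outside the plan in follow-up for that reason. Section 19.7 requires reporting of deaths that occur during the study and does not say whether withdrawn subjects are covered.

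Section 9.3 limits early cases. It excludes anyone for whom "Subject is eligible and scheduled for cardiac resynchronization (CRT) implant" applies, anyone on the active transplant list, and anyone who has or is to receive a VAD. Section 12.1.6.1 nevertheless plans a Cox model for later need of CRT-D, so the plan expects such cases during follow-up.

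**The concern.** Death can be ascertained whatever device is in place, so no measurement reason requires death follow-up to end when the study device does. CRT-D upgrade, VAD and transplant plausibly mark progression of heart failure; explant and investigator discretion need not. If subjects withdrawn for the first group die at a higher rate than those who remain, censoring at withdrawal is informative and the later deaths are missing.

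All-cause death is a secondary equivalence endpoint with margins 0.65 to 1.54. The Synopsis lists it first among the additional endpoints, and the Introduction uses an association between inappropriate ATP and mortality as part of the rationale. The plan also treats two kinds of departure differently: a reprogrammed subject is kept under observation, while an upgraded subject may be dropped.

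**Working it through.** **Inputs from the plan.** N = 2600, 1:1; 10% attrition at 18 months; shock rate 6% (Scenario 1) or 7% (Scenario 2), time base not stated; 42 months' accrual; follow-up 18-60 or 12-54 months (Section 12.1.1.2); final significance level 0.022 (Section 12.3.1).

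**Assumed, because the documents give no figure.** Death 5%/yr before withdrawal and 10-15%/yr after it; 20-50% of non-death attrition falls under the reasons listed above.

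**Step 1: the plan's own figure.** The attrition hazard is -ln(0.9)/1.5 = 0.0702/yr. If the shock rate is an 18-month rate, its hazard is lam = -ln(1-p)/1.5, which is 0.0412 or 0.0484. With h = lam + 0.0702, expected shocks are 2600 x (lam/h) x mean over T of [1-exp(-hT)]. This gives 288.1 and 289.7. Events needed for 90% equivalence power at HR 1 are 4(z(1-a)+z(0.95))^2/ln(0.65)^2 = 280.1 (a = 0.025) or 288.6 (a = 0.022). So 2600 is reproduced with a single 10% exit term.

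Adding a separate 5%/yr death hazard gives 265.9 and 270.0. The match therefore shows that one exit term was used. It does not show whether that term includes death or whether death was left out. It also needs the 18-month reading; an annual rate gives 418-420 shocks. Both attrition readings are carried forward.

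**Step 2: deaths not counted.** Let a be the non-death attrition hazard: 0.0702 - 0.05 = 0.0202 if the 10% includes death, 0.0702 if not. The listed-reason hazard is w = 0.2a or 0.5a, h = a + 0.05, and T is uniform on 18-60 months.

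- Leave alive = 2600 x (a/h) x mean[1-exp(-hT)]
- Counted deaths = 2600 x (0.05/h) x mean[1-exp(-hT)]
- Uncounted = 2600 x mean over T of the integral from 0 to T of w exp(-hu)[1-exp(-d1(T-u))] du, with d1 = 0.10 or 0.15

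The mean of 1-exp(-hT) is 0.2021 (h = 0.0702) or 0.3185 (h = 0.1202).

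| | 10% includes death | 10% excludes death |
|---|---|---|
| Leave alive | 151.4 | 483.7 |
| For listed reasons | 30.3-75.7 | 96.7-241.8 |
| Deaths counted | 374.0 | 344.3 |
| Uncounted, d1 = 0.10 | 4.9-12.3 | 16.1-40.2 |
| Uncounted, d1 = 0.15 | 7.0-17.4 | 22.7-56.8 |

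Uncounted deaths are thus 1-5% of the counted number on the first reading and 5-17% on the second (16.1/344.3 to 56.8/344.3). With baseline death of 3-6%/yr, two to three times that after withdrawal, and the 10% including death, the range is 3-22.

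**Step 3: precision.** SE of the log hazard ratio is 2/sqrt(D). On the first reading it is 0.103 with D = 374.0 and 0.101-0.103 with the missing deaths added; equivalence power at one-sided 0.025 goes from 97.3% to 97.5-97.9%. On the second reading it is 2/sqrt(344.3) = 0.108, against 0.105 (D = 360.4) to 0.100 (D = 401.1).

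**Step 4: bias in the ratio.** With equal withdrawal in both arms the main loss is deaths and precision. For an unequal case, assume listed-reason hazards of 0.5a in one arm and 0.2a in the other, with other attrition 0.65a in both. Listed withdrawals are then 37.7 against 15.2 per 1300 on the first reading and 118.9 against 49.2 on the second. The censored ratio of deaths per person-year is 1.00. Counting the later deaths gives 1.010-1.018 or 1.032-1.059.

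**Step 5: shock-or-death.** With h = a + 0.05 + 0.0412, the first reading gives 4.7-16.6 uncounted deaths against 637.4 events; the second gives 15.3-54.1 against 588.3. On the first reading those subjects would add about 44-117 person-years after withdrawal. At 0.0412 shocks/yr that is about 2-5 shocks that may go unseen, and up to about 16 on the second.

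**The case against.** The strongest reply is that none of this would change a conclusion. The rates are assumed, the largest shift shown in the death ratio is 1.06 against a margin of 1.54, and the trial was sized only for the primary endpoint. That stands, and it sets the priority. The 20-50% share also pools explant and investigator discretion, so the informative part is smaller than the totals.

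The absence of vital status is read partly from silence. Section 10.2 wants every enrolled subject, withdrawn ones included, accounted for; Section 19.7 states no exception for withdrawn subjects; the consent form is not in our copy. The accurate statement is that no such follow-up is specified. An accounting requirement and a phrase about deaths during the study do not supply it. Recording withdrawal reasons and monitoring-committee review could reveal an imbalance but would not recover deaths.

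Stronger readings that a reader might infer do not hold:

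- That every upgraded, transplanted or explanted subject must leave. The list is permissive, so the number withdrawn is unknown.
- That the death comparison is biased towards equivalence. No passage suggests that withdrawal would differ by arm, and the direction of any bias cannot be fixed from the documents.
- That the 10% attrition is known to include death because Section 10.2 lists death as a withdrawal reason. Section 12.1.1.2 does not give its components, and Step 1 fits either way.
- That the primary endpoint is untouched because this point concerns death. Section 12.1.1.3 censors shocks at the same withdrawal date, and an upgraded subject may still have a device that delivers shocks.

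**Conclusion.** The point holds as a low-priority, cheap improvement to the all-cause death endpoint. Followed as written, the plan stops counting deaths at withdrawal, some withdrawal reasons plausibly carry prognostic information, and the resulting analysis falls short of what intention to treat implies for mortality. The size is roughly 5-17 uncounted deaths against 374, or 16-57 against 344, depending on an attrition definition that the documents leave open. It rests on assumed death rates and an assumed share of withdrawals. The shift in the death ratio is about 1.01-1.02 or 1.03-1.06, and only under an assumed imbalance between arms.

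For shock-or-death, adding later deaths while shocks may be unobserved is a trade-off, not a clear gain. For the primary and other shock endpoints, vital status is no remedy; no conclusion is drawn here that they are affected or unaffected.

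**What to change.** - **Section 10.2:** for randomized subjects, separate the end of device follow-up from the end of study follow-up. Collect vital status to study closure unless consent is withdrawn. No clinical or device decision changes.
- **Section 12.1.3.2:** censor death only at consent withdrawal, loss to follow-up or data cut-off. Keep censoring at withdrawal as a sensitivity analysis.
- **Section 12.1.2.2:** keep the planned censoring as the main analysis and count later deaths only in a sensitivity analysis.
- **Section 19.7:** state that deaths of withdrawn randomized subjects are reportable to study closure, within the limits of consent.
- **Reporting:** tabulate withdrawals by reason and arm.

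The cost is an amendment, possibly consent wording, and phone or record checks for roughly 30-76 subjects, or up to about 242 if the 10% excludes death. Sites already make scheduled study calls to remotely monitored subjects (Section 11.7.1), so no new procedure is needed.

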11.7. Subjects who are monitored on LATITUDE

For subjects who are remotely monitored, the wireless LATITUDE[™] Patient Management system will be utilized to collect and store treated tachyarrhythmia episodes. Alerts, diagnostic data, and all treated ventricular episodes EGMs are collected for endpoint evaluation directly from the LATITUDE database. Applicable reports will be uploaded remotely into the study database from the LATITUDE BSC team as defined on the data collection schedule on Table 11.1-2.

After programming to treatment arm (Index procedure Day 0), subjects who are remotely monitored with the LATITUDE system must have the following yellow alerts programmed on in the LATITUDE database:

- Ventricular shock therapy delivered to convert arrhythmia
- Accelerated ventricular arrhythmia episode
- Atrial Arrhythmia burden of at least {>1, 3, 6, 12, 18, or 24} hours in a 24 hour period
- Patient triggered event stored

If the HeartLogic feature is available in the implanted device, all subjects with this feature will be monitored by the LATITUDE BSC team for the specific HeartLogic alerts. In the event of an alert, a report will be uploaded by the LATITUDE BSC team into the study database.

Table 11.7-1: LATITUDE Follow Up Data – Device Report Upload

Data Collection Requirement	Retention of Original Source Documentation
LATITUDE Nominal Device ReportVentricular arrhythmia episodesLATITUDE Alerts	Reports uploaded into the study database by BSC LATITUDE team

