12.1.1.3. Statistical Methods

All implanted and randomized subjects will contribute to the analysis of the Primary Endpoint. Cox proportional hazards modeling will be performed, with time-to-first shock therapy episode used as the outcome and programming scheme used as the covariate in the model. Traditional therapy will be considered the reference group in the analysis. Each subject's first shock therapy episode will contribute to the analysis. Subjects without a shock therapy episode will be censored at their date of death, withdrawal, study exit or on the date of the data snapshot, whichever occurs first. From the Cox model, the hazard ratio and corresponding confidence interval for programming scheme will be calculated. If the confidence interval for the hazard ratio is fully contained within the equivalence region – between 0.65 and 1.54 – equivalence of shocks only and standard programming will be concluded.

If equivalency cannot be established, further testing for superiority will be performed without need for a multiplicity adjustment to the significance level of the test beyond the adjustment necessary to accommodate the interim superiority tests. This additional testing is possible because the equivalence test is comprised of two separate one-sided non-inferiority tests. If non-inferiority is established for only one of the two one-sided non-inferiority tests, superiority can further be tested, per gating methodology.

The following table outlines the possible results and conclusions that can be drawn from the Primary Endpoint analysis.

Result of Lower Confidence Limit of Confidence Interval	Result of Upper Confidence Limit of Confidence Interval	Conclusion
>0.65	<1.54	Equivalence of shocks only to standard therapy
≤0.65	≥1 and <1.54	Non-inferiority of shocks only to standard therapy
<0.65	<1	Superiority of shocks only to standard therapy
≤1 and >0.65	>1.54	Non-inferiority of standard therapy to shocks only
>1	>1.54	Superiority of standard therapy to shocks only

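### A remotely monitored subject can be declared lost on failed contact alone and censored while the device is still sending shock data; the loss of events is small, avoidable and cheap to stop

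*Combined protocol and SAP*

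**What the plan says.** **Withdrawal rule (10.2).** The list of withdrawal reasons includes "Lost to follow-up, despite best efforts to locate the subject". The test for it is "Three documented attempts to contact the subject, including one certified letter, are required to declare a subject lost to follow up". Whether the device is still transmitting plays no part, and remotely monitored subjects are not treated separately. On withdrawal, "Data up to the point of withdrawal will be collected". The only activity described afterwards is that "Normal manufacturer vigilance monitoring of device performance will take place after a subject is withdrawn", which is not endpoint collection.

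**Censoring rule (12.1.1.3).** For the primary endpoint, "Subjects without a shock therapy episode will be censored at their date of death, withdrawal, study exit or on the date of the data snapshot"; the earliest of these dates applies. Sections 12.1.4.2 and 12.1.5.2 use the same rule for appropriate and inappropriate shocks.

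**Data route (11.7, 11.8).** For subjects on LATITUDE, "all treated ventricular episodes EGMs are collected for endpoint evaluation directly from the LATITUDE database". Section 11.8 has the sponsor's LATITUDE team upload treated episodes and leaves a clinic visit to the investigator's discretion. The site's phone call (11.7.1) collects medication changes, adverse events and device deficiencies, but not shocks.

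**Contrast (11.9).** Subjects reprogrammed outside the plan are expressly kept in follow-up to preserve intention-to-treat. Subjects who are unreachable but still transmitting have no such provision.

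**The concern.** The plan has two data-collection schedules but one definition of loss. For subjects seen only in clinic, losing contact does mean losing the shock data. For LATITUDE subjects it need not, because the primary endpoint is device-recorded (12.2.2) and arrives without the subject's help. A subject who stops answering but has not withdrawn consent can be withdrawn and censored while shocks are still reaching the sponsor's system.

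Two things are at stake. First, events are lost that could have been counted without enrolling anyone. Second, the Cox analysis treats censoring as unrelated to shock risk. If people who drop out of contact differ in shock risk, that assumption fails, and following them through the device would avoid relying on it for as long as transmission lasts.

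**Working it through.** **Inputs.** From 12.1.1.2: 2,600 subjects, margin 0.65 to 1/0.65, 90% power, 10% attrition at 18 months, 42 months of accrual, shock rate 6% with 18 to 60 months of follow-up (scenario 1) or 7% with 12 to 54 months (scenario 2). From 8.2: 1:1 allocation. From 12.3.1: final significance level 0.022.

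**Assumptions.** Constant hazards, uniform accrual, true hazard ratio 1. The shock rate has no stated time unit. I read it per 18 months because that reproduces 2,600; read per year, only about 1,790 subjects would be needed.

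**1. Required events** (two one-sided tests):

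D = 4 × (z₀.₉₇₈ + z₀.₉₅)² / (ln 0.65)² = 4 × (2.014 + 1.645)² / 0.1856 ≈ 289. At one-sided 0.025 it is 280.

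**2. Planned events, scenario 1.**
- Shock hazard λ = −ln(0.94)/1.5 = 0.04125 per year.
- Attrition hazard δ = −ln(0.90)/1.5 = 0.07024 per year.
- Expected events = 2,600 × λ/(λ+δ) × (1 − mean of e^(−(λ+δ)u), u from 1.5 to 5 years) = 2,600 × 0.370 × (1 − 0.7005) ≈ 288.
- Subjects needed = 2,600 × 288.6/288.1 ≈ 2,604. Scenario 2 gives about 290 events and 2,590 subjects. The stated 2,600 is reproduced.
- Power = 2Φ(√D/2 × 0.4308 − 2.014) − 1 = 89.9% at 288 events.

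**3. Effect of retention.** Let s be the share of attrition that is loss of contact in subjects who still transmit. Retaining them replaces δ by δ(1 − s). The documents do not give s. I take it as (lost-contact share of attrition) × (share on LATITUDE), with both at 25%, 50% or 75%, so s is 6.25%, 25% or 56.25%.

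| s | Events, scenario 1 | Power | Events, scenario 2 | Power |
|---|---|---|---|---|
| 0 (as planned) | 288.1 | 89.9% | 289.7 | 90.1% |
| 6.25% | 290.2 | 90.2% | 291.5 | 90.4% |
| 25% | 296.6 | 91.0% | 297.1 | 91.1% |
| 56.25% | 307.7 | 92.2% | 306.8 | 92.1% |
| 100% (no attrition at all) | 324.2 | 93.8% | 321.2 | 93.5% |

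Each row assumes that no retained device stops transmitting before study close, so each is an upper bound for its s.

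**4. Width of the interval.** At an estimated hazard ratio of 1 the upper limit is exp(2 × 2.014/√D): 1.268 at 288.1 events, 1.264 at 296.6 and 1.258 at 307.7, against a margin of 1.54.

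**5. The same gain as time.** At month 60 in scenario 1, 2,600 × 0.7005 ≈ 1,821 subjects remain at risk, giving 1,821 × 0.04125/12 ≈ 6.3 events a month. The gain at s = 25% is 296.6 − 288.1 = 8.5 events, or about 1.4 months of follow-up. The gains at 6.25% and 56.25% (2.1 and 19.6 events) are about 0.3 and 3.1 months.

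**The case against.** The strongest reply is that the plan already absorbs this loss. Attrition is in the sample size, and 8.1 and 11.10 close the study when enough shock episodes have occurred, so missing events mean somewhat longer follow-up. That stands. A reader might infer that the power is overstated or that the interval must widen, but the documents support neither.

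The size of the effect also rests on shares that the documents do not give. Section 10.2 lists death, consent withdrawal, explant, CRT-D upgrade and VAD or transplant beside lost contact, so the relevant share could be small. That stands too, and the gain could be near 1%.

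Two readings of the text go too far. A reader might infer that these subjects drop out of the primary analysis. They do not: 12.1.1.3 includes all implanted and randomized subjects, and time and shocks before the withdrawal date count. A reader might also infer that the third failed attempt forces withdrawal. It is a minimum after best efforts, so a site may wait, although nothing tells it to.

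Informative censoring is only a possibility. No section links lost contact to shock risk, assignment is randomized, and subjects are to be kept blinded where reasonable (11.4). The documents give no ground for a bias in a particular direction.

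Finally, retention raises issues of its own. LATITUDE supplies no vital status, so shocks would be captured while deaths might be missed, which matters for the shock-or-death composite. Section 16.4.1 says sponsor personnel do not independently collect critical data. The upload route in 11.7 already exists for every LATITUDE subject, and core-laboratory review (13.3) would continue, but the wording should be checked against that section. These points shape the fix; they do not close the gap.

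**Conclusion.** The concern holds as a limited one. Sections 10.2, 11.7, 11.8 and 12.1.1.3 together allow a consented LATITUDE subject to be censored while the primary endpoint is still being recorded, and no section prevents it. The stated sample size and power are sound. The cost is avoidable loss of events, at most about 2 to 20 of 288 in scenario 1 (power higher by about 0.3 to 2.3 percentage points), or about 0.3 to 3 months of follow-up. It also leaves the analysis relying on non-informative censoring where it need not. These figures depend on the assumed shares, on reading the shock rate per 18 months, and on transmission never stopping. This is a cheap improvement, not a flaw that threatens the trial's conclusion.

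**What to change.** - **10.2:** State that a LATITUDE subject who has not withdrawn consent is not withdrawn as lost to follow-up while the device still transmits, provided the consent form allows it. Keep the three-attempt definition for subjects not on LATITUDE and for those whose transmissions have stopped, and define the withdrawal date for a lost subject, which the plan leaves open.
- **Conduct:** Continue uploads and core-laboratory adjudication. Leave the site's contact attempts and safety follow-up as planned.
- **12.1.1.3, 12.1.4.2, 12.1.5.2:** Censor these subjects at the last transmission for all-cause, appropriate and inappropriate shock.
- **12.1.2.2, 12.1.3.2:** Censor them at the last date vital status is known for shock-or-death and for death.

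**Cost:** a few sentences and possibly a consent line; the upload route and team are in place. Adverse-event, medication and vital-status data will be missing for these subjects while shock data continue, and the report should say so.
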